Appendix A (Section 21.1) provides a schedule of biomarker testing in the study.

Fasting Lipid Profile

A **fasting** lipid profile is obtained at the Screening/Enrollment Visit (Visit 1), Month 2 (Visit 4), Month 4 (Visit 5), Month 12 (Visit 9), annually thereafter and at the CSED Visit.

Non-Fasting Lipid Profile

A **non-fasting** lipid profile will be measured at the Randomization and Month 6 Visits.

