9.5. Study Drug Administration

Participants will self-administer their assigned study drug daily over the course of the study treatment period. Participants will take an oral dose of pemafibrate 0.2 mg or matching placebo tablet twice daily starting the day after completion of Visit 2. Participants may take the study drug in either a fed or fasted state (before or after meals); however, participants should be instructed by the sites to try and remain consistent with the time of dosing for all doses throughout the study. Participants will be instructed by the site to follow dosing instructions on the drug packaging, and to return all remaining unused study drug and packages at the next visit.

Participants will be asked whether there have been any problems with taking the medication, and the investigator will record any significant departure from the dosing instructions (eg, misuse or overdose) as a protocol deviation. For each participant, the number of tablets dispensed, taken, and returned will be recorded on the site's Drug Accountability Log and recorded in the eCRF. Participant compliance will be assessed from information recorded in the eCRF, including study drug count and the start and end date of therapy. Participants will be considered compliant if they have taken $\geq 75\%$ and $\geq 80\%$ of the intended regimen during Placebo Run-In and Treatment Periods, respectively.

Confidential K-877-302 Study Protocol

Version 3 dated 18-Mar-2020

During the active treatment period, if compliance is < 80%, the participant will be counseled by the site on the importance of compliance with the study drug administration.

If a participant has discontinued study drug and the investigator has determined that it is appropriate to re-start study drug, then at the investigator's discretion and with prior approval of either the Sponsor or medical monitor, the investigator may elect to re-start the participant on a once a day dose of study drug with the goal of achieving twice daily dosing.

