To assess the effect of non-informative censoring on the primary outcome, analyses will be performed following the reference-based method outlined by Carpenter, Roger, and Kenward⁶⁹ and detailed in the Statistical Analysis Plan using the piece-wise exponential method described by Lipkovich at al.⁷⁰ For those participants who were lost-to-follow-up, event status after the time of last observation is imputed using the distribution of retrieved dropouts for each arm. Retrieved dropouts are defined as participants who are no longer taking study drug but have agreed to continue to be followed. Other imputation models for missing data will also be explored for their effect on the primary outcome, including models that use the entire placebo group as the reference.

Separate proportional hazards models will also be used to compare the effects of pemafibrate treatment on time to each of the individual components of the composite primary endpoint. Analyses will use methods of competing risks survival analysis and compare the relative effects of randomized treatments on the different components of the composite outcome.^{72, 73} The approach of Lunn and McNeil⁷² provides a readily accessible implementation of a classical approach to competing risk analysis developed by Kalbfleisch and Prentice.⁷⁴

Secondary lipid efficacy endpoints will be analyzed using analysis of covariance (ANCOVA) with a retrieved dropout-based pattern mixture model. Participants with missing data will be imputed using the distribution of retrieved dropouts for each arm, where retrieved dropouts are defined as participants who are no longer taking study drug but have agreed to continue to be followed. Imputed data will be analyzed using an ANCOVA model with baseline measurement as a covariate and the treatment arm and randomization strata as fixed effects.

While all primary analyses are on the ITT population, a Per-Protocol population will also be analyzed which will be limited to participants with no major protocol deviations. Sensitivity analyses for the primary efficacy endpoint will also be conducted examining the effect of compliance and escalation of other lipid-lowering medications. Longitudinal analyses will quantify the impact of pemafibrate on lipid levels, biomarkers of inflammation, and glycemic parameters and other prespecified exploratory lipid and non-lipid biomarkers (Tertiary Endpoints: Section 5.3.1).

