3.2.2.2. Group B: Lipid Endpoints

The Group B lipid efficacy endpoints are:

- 1. The percent change from Screening/Enrollment Visit (Visit 1) to Month 4 Visit (Visit 5) for TG
- 2. The percent change from Screening/Enrollment Visit (Visit 1) to Month 4 Visit (Visit 5) for VLDL-C (calculated). VLDL-C is calculated as TC minus HDL-C minus LDL-C, where LDL-C is measured by a direct homogenous method.
- 3. The percent change from Screening/Enrollment Visit (Visit 1) to Month 4 Visit (Visit 5) for ApoC3
- 4. The percent change from Screening/Enrollment Visit (Visit 1) to Month 4 Visit (Visit 5) for ApoE
- 5. The percent change from Screening/Enrollment Visit (Visit 1) to Month 4 Visit (Visit 5) for HDL-C
- 6. The percent change from Screening/Enrollment Visit (Visit 1) to Month 4 Visit (Visit 5) for non-HDL-C (calculated)
- 7. The percent change from Randomization Visit (Visit 2) to Month 6 Visit (Visit 6) for non-fasting remnant cholesterol
- 8. The percent change from Screening/Enrollment Visit (Visit 1) to Month 4 Visit (Visit 5) for TC
- 9. The percent change from Screening/Enrollment Visit (Visit 1) to Month 4 Visit (Visit 5) for ApoA1

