The total events analysis (second part of endpoint 6) will use negative binomial regression, with outcome being the total number of such events, a log link function, and a subject's total follow-up time as an offset. The independent variable will be randomized treatment assignment, and the

```
Kowa Research Institute, Inc.
Statistical Analysis Plan – Protocol K-877-302 (PROMINENT)
```

model will consider the following variables as fixed effects: sex, prior history of CVD, and statin use at baseline.

The analysis of heterogeneity of treatment effect by PPAR- α genetic polymorphisms will use a Cox proportional hazards model including two stratification variables: sex and prior history of CVD. This is due to both the low level of statin intolerance at baseline and concern that some of the genetic subgroups may be sparse.

In addition to the separate analyses of each component of the primary endpoint, possible heterogeneity in their effects across components will be evaluated. Analyses will use methods of competing risks survival analysis and compare the relative effects of randomized treatments on the different components of the composite outcome^{4, 5}. The approach of Fine and Gray provides a readily accessible implementation of a classical approach to competing risk analysis developed by Kalbfleisch and Prentice⁶.

In addition to the individual components of the composite primary endpoint, other CVD endpoints will be evaluated for treatment effect, including time to all-cause mortality, time to first MI, time to first stroke, time to first ischemic stroke, and time to first hemorrhagic stroke. Analyses will consider both fatal and non-fatal events where appropriate.

Secondary Group B lipid efficacy endpoints will be analyzed using analysis of covariance (ANCOVA) with a retrieved dropout based pattern mixture model. Subjects with missing data will be imputed using the distribution of retrieved dropouts for each arm, where retrieved dropouts are defined as participants who are no longer taking study drug but have agreed to continue to be followed. Imputed data will be analyzed using an ANCOVA model with baseline measurement as a covariate and the treatment arm and randomization strata as fixed effects.

Analysis using an ANCOVA model will be implemented using the SAS® procedure MIXED as follows:

```
PROC MIXED DATA = ...;

CLASS TREATMENT SEX CVD STATIN;

MODEL PCHG = BASELINE TREATMENT SEX CVD STATIN;

LSMEANS TREATMENT / DIFF CL;

RUN;

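### For six of the nine Group B lipid endpoints the ANCOVA leaves out a second pre-treatment value that is already collected; the model is valid, but some precision is lost

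*Protocol*

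**What the plan says.** SAP 3.2.2.2 lists nine Group B endpoints. Eight run from Visit 1 to Month 4; the first is "The percent change from Screening/Enrollment Visit (Visit 1) to Month 4 Visit (Visit 5) for TG". The seventh is different: "The percent change from Randomization Visit (Visit 2) to Month 6 Visit (Visit 6) for non-fasting remnant cholesterol".

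The model has one baseline term. Protocol 14.5 states: "Imputed data will be analyzed using an ANCOVA model with baseline measurement as a covariate". SAP 8.5 says the same and adds the strata: "Imputed data will be analyzed using an ANCOVA model with baseline measurement as a covariate and the treatment arm and randomization strata as fixed effects". The SAS code is "MODEL PCHG = BASELINE TREATMENT SEX CVD STATIN", and its key explains BASELINE only as the baseline value.

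On sampling, Protocol 11.3 has a fasting profile at Visit 1 and a non-fasting "lipid profile will be measured at the Randomization and Month 6 Visits". Protocol 9.5 has dosing "twice daily starting the day after completion of Visit 2". The laboratory schedule in Protocol Appendix A (Section 21.1) marks the lipid panel (TC, TG, HDL-C, calculated non-HDL-C and VLDL-C), direct LDL-C and remnant cholesterol at both Visit 1 and Visit 2. It marks ApoE, ApoA1 and ApoC3 before treatment at Visit 1 only.

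Group B is tested in a fixed order at alpha 0.001, and only after a positive primary result (Protocol 14.5, SAP 8.5).

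**The concern.** A second pre-treatment measurement of the outcome analyte carries information about the participant's usual level that one measurement misses, and randomized treatment cannot have affected it. Adding it as a covariate reduces residual variance without biasing the treatment difference. For six endpoints the plan pays for that measurement and then does not use it in the model: the Visit 2 value for TG, VLDL-C, HDL-C, non-HDL-C and TC, and the Visit 1 value for remnant cholesterol.

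Protocol 14.4 already accepts the principle for the primary endpoint, where it plans covariate adjustment to gain efficiency. At stake are the width of the lipid confidence intervals and, for very small effects, whether a step of the fixed sequence is passed.

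**Working it through.** **What the plan states.** There is no power figure, SD or correlation for Group B. The alpha split adds up: 0.049 + 0.001 = 0.05. The only power figure is for primary events, and it reproduces: 1,276 events by Schoenfeld and 1,283 by Freedman against the stated 1,279 for a hazard ratio of 0.834, and 1,279 × 1.019 = 1,303.3, hence 1,304.

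**Which endpoints have a second value (Appendix A).**

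| Endpoint | In the model | Unused pre-treatment value |
|---|---|---|
| TG, HDL-C, non-HDL-C, TC | Visit 1, fasting | Visit 2, non-fasting |
| VLDL-C (TC minus HDL-C minus direct LDL-C) | Visit 1, fasting | Visit 2, non-fasting; all three parts assayed |
| Remnant cholesterol | Visit 2, non-fasting | Visit 1, fasting |
| ApoC3, ApoE, ApoA1 | Visit 1, fasting | none |

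**Formula.** Let r1 be the correlation of the outcome with the value now in the model, r2 its correlation with the unused value, and r12 the correlation between the two. In units of the outcome variance, the residual is 1 − r1² with one covariate and 1 − R² with two, where R² = (r1² + r2² − 2·r1·r2·r12)/(1 − r12²). If all three equal r, the ratio of residual variances is (1 + 2r)/(1 + r)².

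**Assumed inputs.** The model's own covariate has r1 = r, with r from 0.4 to 0.9. The unused value comes from the other fasting state, so r2 = r12 is taken as r (no penalty), 0.8r or 0.6r.

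Worked case, r = 0.6:
- no penalty: 2.2/2.56 = 0.859, a 14.1% cut;
- 0.8r: R² = (0.36 + 0.2304 − 2 × 0.6 × 0.48²)/(1 − 0.2304) = 0.408; 0.592/0.640 = 0.925, a 7.5% cut.

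| r | No penalty | 0.8r | 0.6r |
|---|---|---|---|
| 0.4 | 8.2% | – | – |
| 0.5 | 11.1% | 6.3% | 3.3% |
| 0.6 | 14.1% | 7.5% | 3.7% |
| 0.7 | 17.0% | 8.1% | 3.8% |
| 0.8 | 19.8% | 7.7% | 3.3% |
| 0.9 | 22.4% | – | – |

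A log-normal simulation, with assumed single-measurement reliabilities of 0.5-0.76 (TG), 0.80-0.93 (HDL-C) and 0.64-0.86 (TC) and a range of extra noise at Visit 2, gave cuts of 4-18%, 7-23% and 9-19%. The overall range is thus about 3-23%. The interval narrows by 1 − √(1 − cut): 1 − √0.967 = 1.7% at the low end and 1 − √0.77 = 12% at the high end.

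**Effect on the tests.** The detectable difference at alpha 0.001 with 90% power and 5,000 per arm is (3.29 + 1.28) × √(2/5000) × residual SD. At r = 0.6 it is 0.0914 × √0.640 = 0.073 SD now, and 0.068, 0.070 or 0.072 SD with the second value (no penalty, 0.8r, 0.6r).

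Power with one and with two covariates, penalty 0.8r:

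| True effect (SD) | r = 0.5 | r = 0.7 |
|---|---|---|
| 0.05 | 34.3% to 37.9% | 58.3% to 64.1% |
| 0.07 | 77.4% to 81.2% | 94.6% to 96.6% |
| 0.10 | 99.3% to 99.6% | 100.0% both |
| 0.15 | 100.0% both | 100.0% both |

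In percentage points, for TC with assumed residual SDs of 20.3 (one covariate) and 19.1 (two), the SE is SD × 0.02 and power is Φ(difference/SE − 3.29): 20% to 25% for a 1.0-point difference, 66% to 74% for 1.5, 95% to 97% for 2.0, and 99.8% to 99.9% for 2.5.

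**The case against.** The strongest reply is that this is a preference, not a defect. ANCOVA on one baseline value plus the randomization strata is valid and unbiased under randomization, nothing in the documents contradicts itself on the point, and most plans could take another prognostic covariate. That stands, and it limits the point to efficiency.

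The fasting state also differs between the two visits. That rules out averaging the values or replacing one with the other, and it makes the gain least certain for TG, VLDL-C and remnant cholesterol. It does not stop the other value from serving as a covariate.

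A reader might infer more than the documents support:

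- *That precision decides how far the Group B sequence runs.* A gain such as 66% to 74% appears only at one assumed effect on the steep part of the power curve. The documents give no Group B effect sizes and do not call any of these effects small. TC is step 8 of 9, so a failure there could cost only TC and ApoA1.
- *That all of Group B is affected.* Three of the nine endpoints have no second value.
- *That Visit 2 lipids are thrown away.* They are the remnant cholesterol baseline and define the non-fasting TG and remnant cholesterol subgroups in SAP 8.3.
- *That the entry limits on TG and HDL-C make the loss worse by truncating Visit 1.* In a normal-model simulation with an assumed eligibility window on Visit 1, the variance ratios barely moved (0.860, 0.830 and 0.803 against 0.859, 0.830 and 0.802 without selection, for r = 0.6, 0.7 and 0.8). Some participants also qualify on the Visit 1.1 retest, with a Visit 1 value outside the limits.

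Finally, the change is more than one extra model term, because missing outcomes are imputed from retrieved dropouts before the ANCOVA. That is right, and the fix allows for it.

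**Conclusion.** The point holds as an optional improvement for TG, VLDL-C, HDL-C, non-HDL-C, TC and remnant cholesterol. It is not an error, and the planned estimates would not be biased.

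The gain is a residual-variance reduction of roughly 3-23%. Every part of that range rests on assumed correlations or reliabilities, since the documents supply none, and a narrower band for any one analyte could not be defended. The benefit is mainly somewhat tighter intervals. Test results would change only for true effects of about 0.05-0.1 SD, and formal testing of Group B takes place only if the primary endpoint is positive.

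A related ambiguity strengthens the case for editing this text. SAP 6.5 sets a default baseline of the latest available value before the first dose, which for TG, HDL-C, non-HDL-C and TC would be Visit 2. The Group B definitions name Visit 1. The specific definition should prevail, but the model code does not say so.

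**What to change.** Before unblinding, amend SAP 8.5 and Protocol 14.5 as follows.

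1. Add the Visit 2 value of the same analyte as a second covariate for TG, HDL-C, non-HDL-C, TC and VLDL-C, forming VLDL-C at Visit 2 as TC minus HDL-C minus direct LDL-C.
2. Add the Visit 1 value as a second covariate for Month 6 remnant cholesterol.
3. Keep the stated reference visits for percent change, and leave the ApoA1, ApoC3 and ApoE models as they are.
4. State that BASELINE means Visit 1, or Visit 2 for remnant cholesterol, notwithstanding the SAP 6.5 default.
5. Include the added covariate in the imputation model so that it matches the analysis model.
6. Give a rule for a missing second value, for example imputing it from the other baseline value without using treatment arm, so that PROC MIXED drops nobody.

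No new samples or assays are needed. The cost is a little extra programming and the missing-covariate rule.

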11.4. Future Genetic Testing

Genetic material (buffy coat or extracted DNA) will be stored for future genetic testing from consenting participants. This sample is further contingent upon local regulations, which may prohibit genetic samples from being collected or shipped outside the country.

Results of genetic testing will not be reported to the participant, relatives, or attending physician and will not be recorded in the participant's medical records. The participant may withdraw consent for genetic testing at any time up to analysis, even after the sample has been obtained. In the event of withdrawal of consent, the biorepository will be notified to pull and destroy the sample.

Confidential K-877-302 Study Protocol

Version 3 dated 18-Mar-2020

For all samples collected for genetic testing, precautions are to be taken to maintain confidentiality by de-identifying the sample with the participant and preventing the genetic data from being linked to the identity of the participant.

Effective from global protocol amendment 2, blood samples collected for genetic testing will be analyzed to investigate whether the effect of pemafibrate as compared with placebo on cardiovascular events differs according to known genetic polymorphisms in the PPARA gene (such as, but not limited to rs6008845).

11.5. Archival of Blood Samples

A **fasting** blood sample will be obtained for archiving at Visit 1 (Screening/Enrollment Visit), a **non-fasting** sample at Visit 2 (Randomization), and a **fasting** sample at Visit 5 (4 months). Total blood draw volumes for these archived specimens will be 22 mL at Visit 1, and 16 mL at each of Visit 2 and Visit 5 visits. The blood samples will be collected only at sites in countries where allowed by local regulations and where approved by the IRB/IEC/REC and relevant regulatory authorities. These blood samples may be used for exploratory purposes.

12. ASSESSMENT OF SAFETY

12.1. Safety Parameters

12.1.1. Vital Signs and Physical Examination

Vital signs will be measured and physical examinations performed at the Screening/Enrollment and Randomization Visits, at all in-person visits conducted during the treatment period, and at the CSED Visit as indicated in the schedule of assessments (Table 4). Vital signs measurements will consist of the following: blood pressure, heart rate, height (Visit 1 and CSED Visit), body weight, and waist circumference; the BMI will be calculated based on baseline height and the most recent recorded weight. Vital signs should be collected after the participant has been resting for 5 minutes in a seated position. To avoid inter-observer variability, every effort should be made to ensure that the same individual who made the initial baseline determinations completes all safety evaluations. Physical examinations will be comprised of a general review of body systems.

12.1.2. Laboratory Assessments

The central laboratory will provide all collection materials and instruction for sample collection, packaging, and shipment.

Where indicated in the schedule of assessments (Table 4) and the Appendix, samples for clinical laboratory procedures will be obtained after fasting for at least 8 hours, when possible and appropriate. For purposes of this study, fasting is defined as nothing to take in by mouth except water and any essential medications (ie, prescribed concomitant medications that may be taken with water only). Prescribed concomitant medications that must be taken with food or after meals should not be taken until after blood sampling.

At Randomization Visit (Visit 2), any participants that have lipid laboratory values outside the exclusionary limits (following retesting) specified in the protocol exclusion criteria (Section 7.2) may not participate further in the study. After randomization, the investigator will be blinded to lipid laboratory test values and only notified if the values exceed clinical alert levels. In this case, clinically appropriate follow-up procedures will occur at the discretion of the investigator.

A detailed summary of laboratory testing is provided in the Appendix.

12.1.2.1. Safety Laboratory Tests

The safety laboratory tests include:

- 1. Chemistry panel including electrolytes (K, Na, Cl), AST, ALT, GGT, alkaline phosphatase (ALP), total bilirubin, direct bilirubin, calculated eGFR, blood urea nitrogen (BUN), CK, total protein, lactate dehydrogenase (LDH), uric acid, and creatinine
- 2. Hematology with complete blood count (CBC), including RBC count, hemoglobin, hematocrit, white blood cell count, white cell differential, and platelet count

- 3. Thyroid studies, including TSH and free T4
- 4. Urinalysis, including creatinine, albumin, and chemistry panel

Safety laboratory testing with the exception of urinalysis will occur at the Screening/Enrollment Visit, Randomization Visit, Months 2, 4, 6 and 12 Visits, at annual visits thereafter, and at the CSED Visit. A urinalysis will be performed at the Randomization Visit, Month 4, and annually thereafter.

Summary statistics of safety laboratory testing will be reviewed by the DSMB in important subgroups such as participants requiring CYP3A and CYP2C8 inhibitors. Based on DSMB review of blood safety data, effective from global protocol amendment 2, the frequency of safety blood laboratory testing after Year 1 (Month 12) will be reduced to once annually, ie, the chemistry panel testing at intervening in-person visits will be discontinued.

12.1.2.2. Reporting of Critical Laboratory Values

Critical laboratory values are values that may warrant medical intervention to avoid possible harm to the participants. Critical laboratory values for the study are defined in the below subsections. The research site will be notified expeditiously (eg, fax, phone, etc.) by the central laboratory in the event of a critical laboratory value (high or low).

12.1.2.2.1. Liver Function Test Elevations

Refer to Section 7.3.1 for details on study drug discontinuation procedures related to elevated liver function results.

Repeat evaluation should include AST, ALT, prothrombin time/INR, total bilirubin, ALP, GGT, creatinine, CK, and complete viral hepatitis screen. The participant should be questioned regarding symptoms, as well as potential causative factors. This information, including results and normal ranges of any laboratory parameters collected at a local laboratory, should be collected on the appropriate eCRF. Hepatobiliary ultrasonography and/or consultation with a hepatologist should be considered if clinically indicated.

Abnormal laboratory parameters should be followed at least weekly (more frequently as clinically indicated) until they have returned to baseline or have stabilized.

